2. OBJECTIVES

Primary Objective:

1. To determine whether SADT-c can be used in patients with COPD to detect SAD.

Secondary Objectives:

- 2. To determine whether the bronze model SADT-a is predictive for SAD in COPD.
- 3. To develop SADT-c.
- 4. To evaluate how SADT-c compares to SADT-a.
- 5. To determine whether oscillometry and spirometry are equally effective for triage diagnosis in patients in primary care with respiratory symptoms.

Exploratory Objective:

Assess the diagnostic performance of the Asthma/COPD Differentiation Classification (AC/DC) Tool.

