6. METHODS

6.1 Study endpoints

6.1.1 Main study endpoint

The primary endpoint is the predictive value of SADT-c for detecting SAD in patients with COPD.

Required variables:

- Diagnosis of Asthma/COPD service
- SAD status defined as R5–R20 > upper limit of normal (ULN)¹
- SADT question results
- Patient characteristics
 - o Age
 - o Sex
 - o Height
 - Body Mass Index (BMI)
 - Age at diagnosis
- Oscillometry and spirometry results

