6.1.2 Secondary study endpoints

The secondary endpoints are:

- 1. Predictive value of SADT-a bronze model for SAD in COPD.
- 2. Agreement between SADT-c results and disease parameters.
- 3. Content validity and reliability.
- 4. Relative predictive value of SADT-a versus SADT-c for SAD in COPD defined as R5– R20 > ULN¹
- 5. Agreement between triage diagnoses from oscillometry and spirometry.
- 6. Relative usability of spirometry and oscillometry.

Required variables:

- 1.
- Triage diagnosis of Asthma/COPD service
- SAD status based on oscillometry test (R5-R20)
- SADT question 8
- Patient characteristics (bronze model)
 - o Age
 - o Sex
 - o Height
 - o Body Mass Index (BMI)
 - Age at diagnosis
- 2.
- Triage diagnosis by Asthma/COPD service
- SAD status based on oscillometry test (R5-R20)
- Lung function results

- Asthma/COPD service collected questionnaires and patient characteristics (as described in chapter 5)
- SADT-c variables
- Patient characteristics bronze model
- 3.
- Cognitive interviews
- SADT-c results
- 4.
- Predictive value SADT-a different models
- Predictive value SADT-c different models
- 5.
- Panel expert diagnoses (spirometry)
- Panel expert diagnoses (oscillometry)
- Patient characteristics
- Difficulty to diagnose (scale)
- 6.
- Operator opinion
- Expert interpreter opinion
- Duration of measurement
- Patient burden

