8.2 Secondary study parameter(s)

SADT-c

To determine whether bronze model SADT-a is predictive for SAD in COPD, the steps described in section 8.1 will be followed. The AUC, LR+ and sensitivity and specificity will be calculated and reported.

To assess the agreement between SADT-c and disease parameters, the steps described in section 8.1 will be reported. Logistic regression analysis results will be reported.

To assess the content validity and reliability of the SADT-c, 10-15 patients with COPD and SAD will be invited for a cognitive interview. Results will be presented in a descriptive way.

To evaluate how SADT-c and SADT-a compare in detecting SAD in COPD the predictive values of the various SADT-c and SADT-a models will be compared.

In case the SADT-c has a significantly reduced predictive value as compared to the SADT-a, new items derived from the cognitive interviews will be added, if any. The amended questionnaire will subsequently be reinvestigated using the same protocol, in the same population (ie. 100 patients with COPD participating in the SCOOP study).

Oscillometry vs spirometry

To assess the agreement between oscillometry and spirometry, triage diagnoses as determined by the expert panel will be compared. Cohen's kappa or comparable statistics will be used to compare the outcomes. Additional analysis will be done adjusted for difficulty of diagnosis and the agreement between panel members. In addition, subgroup analysis will be performed based on the level of agreement between panel members.

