9.3 Benefits and risks assessment, group relatedness

The risks associated with participating the SCOOP-study are negligible because besides the usual procedures at the Asthma/COPD service, the study concerns a non-invasive test and questionnaire.

The overall aim of the study is to evaluate whether the SADT-c can be used to determine SAD in patients with COPD, similarly to how the SADT-a is used in patients with asthma. The analyses at the end of the study will conclude its applicability for patients with COPD.

Additionally, oscillometry is a non-invasive technique that requires only 45-60 seconds of tidal breathing. Should the results demonstrate equivalent effectiveness in the diagnostic work-up of respiratory symptoms, patients in primary care might experience a reduced burden during diagnostic testing in the future.

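### Objective 5 asks whether oscillometry and spirometry are equally effective, but its diagnostic endpoint and analyses measure only agreement between them, with no reference diagnosis

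*Protocol*

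**What the plan says.** Protocol section 2 gives objective 5 as: "To determine whether oscillometry and spirometry are equally effective for triage diagnosis in patients in primary care with respiratory symptoms". The Summary's rationale describes the same work as a comparison of the diagnostic accuracy of the two tests. The Summary's paragraph on burden and risks refers to oscillometry being proven equally effective. Section 9.3 looks ahead in similar terms: "Should the results demonstrate equivalent effectiveness in the diagnostic work-up of respiratory symptoms", after which patients might face less testing burden.

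Section 6.1.2 ties two endpoints to this objective: "Agreement between triage diagnoses from oscillometry and spirometry" and "Relative usability of spirometry and oscillometry". The variables required for the first are the two panel diagnoses, patient characteristics and a difficulty score. None of them is a reference diagnosis.

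Section 8.2 plans the analysis: "Cohen's kappa or comparable statistics will be used to compare the outcomes". It adds: "Additional analysis will be done adjusted for difficulty of diagnosis and the agreement between panel members". It also states that "subgroup analysis will be performed based on the level of agreement between panel members". Section 8 describes no analysis of usability.

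Under section 6.3, three experts each read one test's report for a patient and, at least four weeks later, the other test's report. The same medical history and questionnaires accompany both. Two more experts are added only when exactly two of the three diagnoses match.

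**The concern.** Effectiveness or accuracy of a diagnostic test has to be judged against something. The objective and the Summary use those terms, while the endpoint and the analysis compare one test only with the other. Agreement is symmetric: exchange the two tests and it is unchanged. It therefore cannot separate two equally good tests from two equally poor ones, or either from a pair in which one is clearly better.

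The design blurs the reading further. The same experts see the same history and questionnaires with both reports, so some agreement can arise from information that neither test supplies.

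At stake is how objective 5 is reported. A respectable kappa could be presented as evidence of equal effectiveness in primary care when the data do not bear on that question.

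**Working it through.** The protocol gives no target kappa, margin or sample size for objective 5, so there is no figure to reproduce. Section 4.4 sizes the primary prediction model only. The check asks what a given agreement implies about accuracy.

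**Inputs.** From the protocol: 200 participants, each with a panel diagnosis from each test. Assumed for illustration: two diagnostic classes split 50:50 (100 of 200 are expected to have COPD), a hypothetical true diagnosis, and errors equally likely in both classes. Chance agreement Pe is then 0.50.

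**1. Same kappa, different accuracy (independent errors).** Agreement Po = a1·a2 + (1 − a1)(1 − a2), and kappa = (Po − Pe)/(1 − Pe).
- Both tests 90% accurate: 0.9 × 0.9 + 0.1 × 0.1 = 0.82.
- One test 100% accurate, the other 82%: 1.0 × 0.82 + 0 × 0.18 = 0.82.
- In both cases kappa = (0.82 − 0.50)/0.50 = 0.64.

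**2. The same without assuming independent errors.** Hypothetical counts for 200 patients:

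| Both correct | Only spirometry correct | Only oscillometry correct | Both wrong | Spirometry accuracy | Oscillometry accuracy | Po | Kappa |
|---|---|---|---|---|---|---|---|
| 140 | 20 | 20 | 20 | 80% | 80% | 0.80 | 0.60 |
| 140 | 40 | 0 | 20 | 90% | 70% | 0.80 | 0.60 |
| 140 | 0 | 40 | 20 | 70% | 90% | 0.80 | 0.60 |
| 60 | 20 | 20 | 100 | 40% | 40% | 0.80 | 0.60 |
| 100 | 50 | 50 | 0 | 75% | 75% | 0.50 | 0.00 |

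The first four rows share kappa 0.60 and differ completely in accuracy. The last row shows two equally accurate tests with kappa 0.

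**3. What agreement does bound.** The difference in accuracy cannot exceed 1 − Po. In the two-class setting that is 20 percentage points at kappa 0.6, 10 at 0.8 and 5 at 0.9. It limits the difference, but gives neither its direction nor the level of accuracy.

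**4. Precision at n = 200, kappa 0.60.** Half-width = 1.96 × √[Po(1 − Po)/n]/(1 − Pe), with Po = Pe + 0.60(1 − Pe).
- Pe = 0.50: Po = 0.80; 1.96 × √(0.80 × 0.20/200)/0.50 = 0.111, an interval of about 0.49 to 0.71.
- Pe = 0.25: Po = 0.70; 1.96 × √(0.70 × 0.30/200)/0.75 = 0.085.
- Pe = 0.35: Po = 0.74; 1.96 × √(0.74 × 0.26/200)/0.65 = 0.094.

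The last two apply if more diagnostic categories bring chance agreement down to 0.25–0.35. Sampling error is moderate. The main ambiguity is that in steps 1 and 2, and a larger sample would not remove it.

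**The case against.** The strongest reply is that the analysis fits its declared endpoint. Section 6.1.2 makes agreement the endpoint, and kappa is a suitable statistic for agreement. That stands. The fault lies between the objective's wording and the endpoint, not in the choice of kappa.

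A reader might also infer more than the text supports:

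- **That kappa is the only analysis.** It is not. Comparable statistics, adjusted analyses and subgroup analyses are foreseen, and usability is a second endpoint. However, the added analyses are still of agreement, and usability does not measure diagnostic effectiveness.
- **That the protocol commits itself to concluding equivalence, or to replacing spirometry.** Section 9.3 and the Summary's burden paragraph are conditional statements about possible benefit. Nowhere does the protocol say that oscillometry will replace spirometry.
- **That the missing kappa cut-off is itself a defect.** A threshold can be left to the statistical analysis plan, which is not at hand. It is not part of this point.

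The unseen plan does not settle the rest. Section 8 says it will describe in more detail the analyses already set out there, and those estimate agreement. Filling in technical detail would not turn that into accuracy.

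Finally, independent errors are unlikely with shared readers and shared history. That is fair against step 1 as a model of this trial, but step 2 reaches the same result without the assumption.

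**Conclusion.** The point holds as an inconsistency within the protocol. The objective and the Summary speak of equal effectiveness and diagnostic accuracy; the endpoint and analyses deliver agreement between two panel diagnoses, without a reference. A kappa of 0.64 is as compatible with 90% against 90% accuracy as with 100% against 82%. A kappa of 0.60 allows a 20-point difference in either direction. These figures rest on two balanced classes with symmetric errors and are illustrations, not forecasts. The symmetry of agreement does not depend on them.

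Very high agreement would show that the two tests lead to similar diagnoses, which is useful. It would not show that the diagnoses are right, and part of it could come from the shared readers, history and questionnaires. The objective is secondary, so the primary analysis is untouched. The correction should still be made, because it changes what the trial may conclude at almost no cost.

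**What to change.** **Wording.** Restate objective 5 as agreement or interchangeability of the triage diagnoses from the two tests. Change the Summary's diagnostic-accuracy sentence and the conditional statements in the Summary and section 9.3 to match.

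**A benchmark from reads already planned.** Use the individual initial reads of the three experts:
- agreement between different readers across tests (reader A on spirometry against reader B on oscillometry): 3 × 2 = 6 pairs per patient;
- agreement between different readers within spirometry: 3 pairs per patient.

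Report the difference with a bootstrap 95% confidence interval, resampling patients. This asks whether changing the test as well as the reader adds disagreement beyond changing the reader alone. Leave out the two additional experts' reads, which are triggered by the initial result.

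Do not benchmark same-reader agreement across tests against different-reader agreement within spirometry. The first holds the reader's habits constant and the second does not, so interchangeability could be favoured falsely. The like-for-like comparator would be a repeat spirometry read by the same expert, which is not planned. Even the matched comparison speaks only to interchangeability when history and questionnaires are available to the reader.

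**Service diagnosis.** The variable listed in section 6.1.1 as "Diagnosis of Asthma/COPD service" may be compared with each panel diagnosis descriptively. It cannot serve as a neutral reference, because spirometry is part of the service visit and informs that diagnosis.

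**Cost.** Edits to a few sentences and a modest extra analysis, with no new patients or reads. The permitted conclusion is weaker than equal effectiveness. Keeping the stronger claim would require a defined reference diagnosis and a margin, neither of which the protocol supplies.

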8.3 Other study parameters

To assess the diagnostic performance of AC/DC tool, the diagnoses based on the tool will be compared to the diagnoses given by the expert panel. Results will be compared using logistic regression analysis.

9. ETHICAL CONSIDERATIONS

9.1 Regulation statement

This study will be conducted in accordance with the principles of the declaration of Helsinki (version October 2013).

9.2 Recruitment and consent

The informed consent process will follow the principles outlined in the current version of the Declaration of Helsinki.

Prior to the visit, when the Asthma-COPD service sends the initial invite to patients, potentially eligible participants will be invited by the study sites through an information leaflet (document "E3. Flyer"). It will be made clear that the study is not part of the Asthma-COPD service regular care and that choosing to participate (or not) will not influence the patient's care. The information leaflet specifies different ways in which participants can obtain additional information, ask questions, or indicate their interest in participating the study.

The Healthcare Professional (HCP) from the Asthma/COPD service will explain the nature of the study with the participant after they have shown interest in participating. Participants will then receive either a digital or hard copy of the Patient Information Sheet and Informed Consent Form (ICF) (Document E1/2. ICF). Participants must be informed that their participation is voluntary, and they are free to refuse participation and may withdraw their consent at any point during without any consequences.

Before signing, participants will have the opportunity to ask any questions they might have. Upon satisfactory clarification of all questions, participants will be given the option to sign the ICF. The signing will be done in person at the study site by both the participant and the HCP. Following the signing process, one copy of the ICF will be kept at the site in line with Good Clinical Practice (GCP) standards, and the other copy will be given to the participant.

9.3 Benefits and risks assessment, group relatedness

The risks associated with participating the SCOOP-study are negligible because besides the usual procedures at the Asthma/COPD service, the study concerns a non-invasive test and questionnaire.

The overall aim of the study is to evaluate whether the SADT-c can be used to determine SAD in patients with COPD, similarly to how the SADT-a is used in patients with asthma. The analyses at the end of the study will conclude its applicability for patients with COPD.

Additionally, oscillometry is a non-invasive technique that requires only 45-60 seconds of tidal breathing. Should the results demonstrate equivalent effectiveness in the diagnostic work-up of respiratory symptoms, patients in primary care might experience a reduced burden during diagnostic testing in the future.

10. ADMINISTRATIVE ASPECTS, MONITORING AND PUBLICATION

10.1 Handling and storage of data and documents

Data handling and storage will comply with the General Data Protection Regulation (GDRP). The investigator will ensure protection of participant's personal data in compliance with the Personal

Data Protection Act and that all reports, publications, and any other study disclosures do not reveal the identity of the participant, except where required by laws. Participants are identified only by a participant identification number or site identification number to maintain participant confidentiality. All participant study records will be kept safely in an access-controlled area. Identification code lists linking participant names to participant identification numbers will be stored separate from participant records. In case of data transfer, the sponsor or its representative will maintain high standards of confidentiality and protection of participant personal data. Clinical information will not be released without the written permission of the participant, except for monitoring by clinical quality assurance auditors or other authorized personnel appointed by the sponsor, by appropriate IRB members, and by inspectors from regulatory authorities.

10.2 Public disclosure and publication policy

Findings of the study will be presented as an abstract at (inter)national conferences and published. In our publications, the identity of the patients will not be disclosed in any way.

